4. How helpful were components of the ISP (getting feedback on level of distress, being able to dialogue with clinician re: concerns, and having specific resources offered) according to participants in the ISP who came for initial intake at RFWP?

- a. Prior ISP studies with undergraduate and graduate samples (e.g., Haas et al., 2008) would suggest that the online dialogue with a clinician re: concerns will be rated as especially helpful and instrumental to ISP participants who eventually sought treatment.
- 5. How many residents, fellows, and faculty show significant change in their levels of distress and burnout while in treatment at the RFWP? What demographic variables (gender, ethnicity), training/work variables (trainee/faculty status, type of program, year of training) are associated with change in distress and burnout ratings across treatment?
- 6. Is dose of treatment (# of sessions over 12 month period) associated with lower risk of quitting training program, leaving faculty position or leaving clinical medicine as a field?
- 7. At intake, what is the association between descriptive variables (i.e., demographics, programmatic factors), level of distress, burnout, and intent to quit medicine and/or training program or faculty position? Is dose of treatment (number of sessions over a 12 month period) associated with lower risk of quitting training program or faculty position?
 - a. Questions about intent to quit will be based on Boroff et al. measure used by employers and now being used in healthcare setting (e.g., OHSU Pulse Survey).
 - b. Status in training program, faculty position will be based upon clinician rating in last session.
- 8. How do consumers of RFWP services compare to the overall Providence, Legacy and OHSU population of trainees and SOM faculty in terms of demographics, program type? Are they representative?
 - a. Hypothesis: This first question is exploratory as little research exists on specific rates of recovery (e.g., decrease in distress) in health care providers in counseling/coaching. In general outpatient clinics, there are no gender or racial/ethnic differences in response to high quality mental health services (e.g., Lambert , 2007).
 - b. Hypothesis: the 2nd question—prior studies with a general population would suggest that women and primary care physicians, will be more likely to have sought counseling.

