ISP Sample of Residents, Fellows, and Faculty: All OHSU residents and fellows (approximately 800 annually) and all full-time (0.5 FTE) faculty (approximately 3000) will be sent via OHSU email a link to the ISP survey following the RFWP clinician's presentation of the Stress and Depression workshop to their department. Note: only residents, fellows and full-time SOM faculty will be included as they are the only ones who are eligible for services through the RFWP (we don't have capacity to provide services to all adjunct faculty). All Legacy residents (approximately 90 a year) will be invited by RFWP clinicians (during workshops/orientation to these groups) to participate in completing the ISP. Note: new Legacy residents/fellows effective 7/1/21 will no longer be enrolled. All Providence residents (approximately 90 a year) will be invited by RFWP clinicians (during workshops/orientation to these groups) to participate in completing the ISP. *RFWP Client Outcomes Sample:* All patients seen at the RFWP (to start with IRB approval) will be invited to participate in the research study—estimated to be 200-300 annually that are seen at the program. This estimate is based on 17% of 800 OHSU residents/fellows and approximately 2% of 3000 SOM faculty utilizing services through the RFWP in 2012-13. Increased outreach efforts through this proposed project “Reaching Out” will likely raise the visibility of the RFWP (especially among faculty) and lead to a slightly higher number of faculty and medical trainees utilizing future RFWP annually.

All clinical data are entered into an encrypted ACCESS clinical records database that only RFWP clinicians have permission to access. Participants who also complete the Research Study Consent Form will have the following clinical data exported into a research database for analyses: RFWP Subject ID number* randomly assigned (by computer) to the resident, fellow, or faculty member at time of intake,

- demographic and work/training program information (gender, year of birth, ethnic/race, year of training if relevant, resident/faculty status, type of program/specialty) from the “Personal History and Data Form” completed by the patient in the first meeting
- reason for referral, referral source, knowledge of RFWP
- psychological, suicide, and medication history (if relevant) based on clinical interview
- participation in the ISP and ratings of helpfulness of the ISP components (in “Personal Health History and Data Form”)

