Statistical analyses will be conducted by [name] and her research team and will consist of descriptive analyses (e.g., frequencies, means, standard deviations), correlational analyses, and some multiple regression analyses to determine whether participation in the ISP is predictive of engagement in treatment and recovery from depression, substance abuse, or suicide risk. In addition, pre-post comparisons of risk, distress and burnout levels will be conducted in relation to demographic and treatment factors for all participants in the RFWP. Additional analyses will be conducted comparing participants to overall Providence and OHSU SOM populations on demographics to see if samples are representative of their institution's eligible population.

References

ACORN, Collaborative Outcomes Resource Network. <https://psychoutcomes.org>.

Accreditation Council for Graduate Medical Education. ACGME institutional requirements.

http://www.acgme.org/acgmeweb/Portals/0/irc_IRCpr07012007.pdf. Updated 2007. Accessed November 4, 2012.

American Medical Association. Physician suicide webinars. <http://www.ama-assn.org/pub/physician-resources/physician-health/physician-suicide>. Accessed 11/20/2011.

Boroff, K. E., & Lewin, D. (1997). Loyalty, Voice, and Intent to Exit a Union Firm: A Conceptual and Empirical Analysis. *Industrial and Labor Relations Review*, 51(1), 50-63.

Drum, DJ et al. New data on the nature of suicidal crises in college students: Shifting the paradigm. *Professional Psychology*. 2009; 40, 213-222.

Ey S, [name] M, Kinzie JM, Choi D, Girard DE. "If you build it, they will come": Attitudes of medical residents and fellows about seeking services in a resident wellness program. *JGME*. 2013 (Sept).

Gallagher RP. *National Survey of Counseling Center Directors*. Monograph Series Number 80. Alexandria, VA: International Association of Counseling Services. 2005.

Gaynes BN et al. Screening for suicide risk in adults: A summary of the evidence for the US preventive services task force. *Ann Intern Med*. 2004; 140: 822-835.

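### Research Question 8 and hypothesis 8b ask who uses the RFWP, but the data reach the analysis only for clients who also consent to research, so help-seeking and consenting cannot be separated

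*Protocol*

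**What the plan says.** **The question.** Research Question 8 in the protocol asks "How do consumers of RFWP services compare to the overall Providence, Legacy and OHSU population" in demographics and type of program. Hypothesis 8b expects that "women and primary care physicians, will be more likely to have sought counseling". The target group is everyone who came to the RFWP.

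**The data.** Under Data Collection, Sample and Measures, the protocol states: "Participants who also complete the Research Study Consent Form will have the following clinical data exported into a research database for analyses". The exported items include "demographic and work/training program information (gender, year of birth, ethnic/race, year of training if relevant, resident/faculty status, type of program/specialty", which are the variables that Research Question 8 needs. Clients outside the research stay in the clinical system: "All clinical data are entered into an encrypted ACCESS clinical records database that only RFWP clinicians have permission to access".

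**The consent.** The section on consent and privacy makes research consent a form separate from treatment consent and provides for clients who do not want to join the outcomes study. Data Collection says that all patients are invited to take part.

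**The comparison.** The SOM Summary Data section requests aggregate figures on the whole trainee and faculty population. It requests none on all RFWP users. Statistical Analyses then plans "comparing participants to overall Providence and OHSU SOM populations on demographics to see if samples are representative" of the eligible population.

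**The concern.** A client appears in the Research Question 8 comparison only after two steps: coming to the RFWP and agreeing to research. The research question and 8b concern the first step alone. If the second step differs by gender, ethnic group or specialty, a gap between the sample and the institution may come from consent rather than help-seeking. Equally, a true difference in help-seeking may be hidden.

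At stake is the interpretation of one research question and one directional hypothesis. Hypothesis 8b could appear supported or unsupported for a reason unrelated to who sought counseling, and the data in the research database could not show which had happened. A later SAP could define the comparison more closely, but it could not recover demographics that were never exported.

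**Working it through.** **1. The protocol's own figure.** Data Collection expects 200–300 clients a year, based on "17% of 800 OHSU residents/fellows and approximately 2% of 3000 SOM faculty utilizing services". The arithmetic is 0.17 × 800 + 0.02 × 3,000 = 136 + 60 = 196, which reproduces the lower end. The protocol shows no arithmetic for the upper end.

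**2. What the comparison estimates.** For two groups A and B of clients:

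apparent ratio of representation (A to B) = true ratio of help-seeking × (consent rate in A ÷ consent rate in B).

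The second factor is 1 only if the two groups consent at the same rate. The protocol gives no consent rate, overall or by group.

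**3. Illustration.** These inputs are assumptions: the institution is half women, there is no true difference in help-seeking (so 98 women and 98 men among 196 clients), and the consent rates are as listed. Share of women = 98·c_w ÷ (98·c_w + 98·c_m). The z value sets that share against 50%, with standard error √(0.25 ÷ number of consenters).

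| Consent, women/men | Consenters | Share of women | Apparent ratio | z, one year |
|---|---|---|---|---|
| 80%/80% | 78.4 + 78.4 = 156.8 | 50.0% | 1.00 | 0 |
| 90%/80% | 88.2 + 78.4 = 166.6 | 52.9% | 1.13 | 0.76 |
| 80%/60% | 78.4 + 58.8 = 137.2 | 57.1% | 1.33 | 1.67 |
| 60%/80% | 58.8 + 78.4 = 137.2 | 42.9% | 0.75 | −1.67 |

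**4. Would a test declare it?** At 80%/60%, z = 1.67 gives p of about 0.09, so the expected one-year result is not significant. The chance that a two-sided 5% test rejects is about Φ(1.67 − 1.96) = 39%. If the same gap persisted over five pooled years (a further assumption), there would be 5 × 137.2 = 686 consenters, z = 3.74, and a chance of about Φ(3.74 − 1.96) = 96%. Pooling does not remove a bias of this kind. It makes the wrong answer more certain.

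**5. The other direction.** A true help-seeking ratio of 1.30 with 60%/80% consent appears as 1.30 × 0.60 ÷ 0.80 = 0.975, so the pattern that 8b predicts would disappear.

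**The case against.** **There is no evidence that consent varies.** This is correct. A reader might infer unequal consent from the resident survey described under Purpose/Aims, where concerns differed by subgroup. Those differences were about finding time away from duty (women, primary care) and about whether counseling would help (ethnic minority and male residents). They are barriers to coming for counseling, and they say nothing about a client already in treatment agreeing to research. The same survey found fewer concerns about confidentiality than at other centers.

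**The plan may reduce the problem.** All patients are invited, the form may be signed at a later session and then covers earlier data, and a Certificate of Confidentiality protects the records. These features may raise consent and narrow any gap. Late signing also gives clients who attend longer more chances to enter. None of this shows that consent is even across groups.

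**The word *participants* is loose.** The section on withdrawal uses it for anyone receiving services, so Statistical Analyses might mean all users. Even then, the protocol describes no route by which the demographics of non-consenting clients reach the analysts. Other sentences can be read as every client signing both forms. They have to be read beside the invitation and the stated right to decline.

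**Representativeness of the analyzed sample is a proper question.** It is, and the consented sample is the right one for it. That comparison does not answer who sought counseling.

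**Consent rates belong in a SAP or a participant-flow report.** Agreed. Their absence is not the fault raised here. The fault is the mismatch between the research question and the export rule, and the protocol itself fixes both.

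**Conclusion.** The mismatch is real. As written, the protocol answers a question about all service users with data on consenting users, so its comparison estimates help-seeking multiplied by consenting.

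The size and direction of any bias are unknown. In the illustration the share of women runs from 42.9% to 57.1% where the truth is 50%. That range depends entirely on the assumed consent rates and the assumed 50/50 split. If consent is unrelated to demographics and program type, there is no bias.

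Two stronger readings are tempting, and the documents support neither. One is that the comparison measures consent instead of help-seeking. It measures the product of the two. The other is that 8b will be falsely confirmed. Nothing in the protocol shows that consent differs by group, and even the 80%/60% case is not expected to be significant in a single year.

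The point limits what can be concluded from Research Question 8 and 8b. It does not bear on participant safety.

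**What to change.** 1. Subject to IRB agreement, have the RFWP clinicians produce an aggregate, de-identified count of **all** clients from the existing clinical database. Give it by gender, ethnic/racial group, trainee/faculty status and the five specialty groups already used for the SOM summary data. IRB agreement is needed because the count includes clients who declined research.
2. Report one-way margins only, pool years where cells are small, and suppress cells so that decliners cannot be derived by subtracting the consented sample. The risk is real: 60 faculty users a year over five specialty groups average 12 per group.
3. Compare this table with the SOM summary data to answer Research Question 8 and 8b. Keep the comparison of the consented sample with the institution, and label it as a check on whether the analyzed sample is representative.
4. If the IRB does not permit the count, reword Research Question 8 and 8b to describe consenting research participants only, and draw no conclusion about who sought counseling.

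**Cost:** a small yearly tabulation, an IRB amendment with matching protocol wording, and loss of detail in small groups. The program already states overall utilization percentages, but the protocol shows no breakdown by these variables and says that faculty rates were still to be evaluated, so the tabulation would be new work.

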When the ISP has been completed by an individual, the ISP computer immediately analyzes the responses on the questionnaire and classifies the questionnaire into 3 Tiers according to level of distress on the PHQ-9 (a standard depression screen) and level of suicide risk with Tier 1 (highest risk) and 3 (lowest risk). Clinicians are able to review answers to each question and the open-ended question re: recent stressors. The ISP protocol requires clinicians to respond to Tier 1 respondents within 24 hours, Tier 2 in 36 hours and Tier 3 in 48 hours. The clinician sends a response specific to the respondent's tier, introduces himself/herself (provides email, pager) and offers responses. For Tier 1 and 2 respondents, the clinician will urge them to schedule an in-person meeting via official OHSU email or the clinician's pager. For Tier 3 respondents, the clinician may offer an in-person meeting and/or educational/preventive resources (e.g., websites/handouts via the message posted). All respondents will be given the option to dialogue further with the clinician about any concerns/questions they might have via posting responses on the ISP website to the clinician and respondent. Once the clinician posts a response, the computer accesses the respondent's encrypted email address and send a notification that a response is available for viewing. Several reminders will be sent automatically to Tier 1 and 2 students and then 15 and 30 days after the clinician's response is posted. If they did not contact the clinician, a final brief update questionnaire is sent to the respondent to ask about how he/she is doing in the past few weeks and ask about possible reasons for not responding the clinician's invitation to dialogue or meet. Respondents can dialogue with the RFWP clinician as frequently as they need to although the goal is to address their concerns and facilitate them coming in for an in-person evaluation at the RFWP.

An ISP database will be created with this de-identified data for each participant that completes the ISP and will include the responses on their ISP, Tier status, any communications between the participant

and the RFWP clinician and whether he/she accepted a referral for services and expressed willingness to schedule an in-person evaluation at the RFWP. Note: no identifying information will be included in the ISP database other than gender, broad categories of year of training or faculty status, broad category of age and type of program (e.g., primary care vs. nonprimary care). If the participant reveals his/her name in any communications with the RFWP clinician, this data will be deleted from the ISP database. Appointments will be scheduled outside of the ISP system by instructing the participant to contact the RFWP clinician directly via OHSU email and at that time revealing who they are.

At the first in-person or telehealth (during modified operations under COVID-19, all RFWP visits became telehealth) appointment at the RFWP, the client will be asked to review and sign a (1.) consent form to participate in treatment at the RFWP and (2.) a research consent form. Clients may be given a copy of the research consent form to review and then be given the option to sign the research consent form in subsequent sessions. The research consent form will include wording that the client is giving permission for retrospective data (prior to signature on research consent form) to be included in the study. Due to all visits now being telehealth, the intake paperwork and research consent forms are presented and reviewed in the telehealth session and client then can complete them and email them back to the clinician via secure OHSU email.

RFWP Client Outcomes Protocol: After completing (1.) an informed consent to be in treatment at the RFWP and (2.) a research consent form, all patients being seen at the RFWP (referred by ISP, other referral sources or self-referred) will be asked to complete a brief measure of a level of distress, burnout, level of risk and treatment history and needs. Specifically, the ACORN (a psychometrically sound, standardized 13-item measure of psychological distress within the past 2 weeks) and 2 screening questions for emotional exhaustion and depersonalization from the Maslach Burnout Inventory (MBI) will be given at the first session and subsequent sessions to measure client progress in treatment. The Maslach Burnout Inventory (MBI) is a psychometrically sound measure often used with health professionals; West and colleagues (2009) found that 2 items are highly predictive of physician burnout as a quick screen. Clinicians will review with their patients how they responded to these questionnaires—as one indicator of their response to treatment. This type of regular brief assessment and collaborative discussion with patients about their progress in mental health treatment has been shown to be highly effective in preventing patients from prematurely terminating from treatment and in facilitating the delivery of tailored, relevant interventions with patients (e.g.,<https://psychoutcomes.org>; Lambert, 2004). Patients will also complete the Flourishing Scale (a positive psychology measure that asks about whether patients feel their activities are meaningful, whether they feel optimistic about their future, feel respected). This measure is correlated with life satisfaction.

Patients also will be invited out to fill out a psychometrically sound measure of patient satisfaction, the Client Satisfaction Questionnaire (CSQ-8; Atkinson, 1979) on their level of satisfaction with services at the RFWP. They will be asked to fill the CSQ-8 out anonymously and mail back the survey or put it in a locked drop box in the waiting room areas.

Note: At the time of treatment, clients will be asked if they completed the ISP and whether it was helpful to get feedback on their level of distress and to be able to dialogue with a clinician. **Data Collection**

Sample and Measures

ISP Sample of Residents, Fellows, and Faculty: All OHSU residents and fellows (approximately 800 annually) and all full-time (0.5 FTE) faculty (approximately 3000) will be sent via OHSU email a link to the ISP survey following the RFWP clinician's presentation of the Stress and Depression workshop to their department. Note: only residents, fellows and full-time SOM faculty will be included as they are the only ones who are eligible for services through the RFWP (we don't have capacity to provide services to all adjunct faculty). All Legacy residents (approximately 90 a year) will be invited by RFWP clinicians (during workshops/orientation to these groups) to participate in completing the ISP. Note: new Legacy residents/fellows effective 7/1/21 will no longer be enrolled. All Providence residents (approximately 90 a year) will be invited by RFWP clinicians (during workshops/orientation to these groups) to participate in completing the ISP. *RFWP Client Outcomes Sample:* All patients seen at the RFWP (to start with IRB approval) will be invited to participate in the research study—estimated to be 200-300 annually that are seen at the program. This estimate is based on 17% of 800 OHSU residents/fellows and approximately 2% of 3000 SOM faculty utilizing services through the RFWP in 2012-13. Increased outreach efforts through this proposed project “Reaching Out” will likely raise the visibility of the RFWP (especially among faculty) and lead to a slightly higher number of faculty and medical trainees utilizing future RFWP annually.

All clinical data are entered into an encrypted ACCESS clinical records database that only RFWP clinicians have permission to access. Participants who also complete the Research Study Consent Form will have the following clinical data exported into a research database for analyses: RFWP Subject ID number* randomly assigned (by computer) to the resident, fellow, or faculty member at time of intake,

- demographic and work/training program information (gender, year of birth, ethnic/race, year of training if relevant, resident/faculty status, type of program/specialty) from the “Personal History and Data Form” completed by the patient in the first meeting
- reason for referral, referral source, knowledge of RFWP
- psychological, suicide, and medication history (if relevant) based on clinical interview
- participation in the ISP and ratings of helpfulness of the ISP components (in “Personal Health History and Data Form”)
